### **7.3.3 Withdrawal of patients from treatment or study**

#### **7.3.3.1 Withdrawal from treatment**

A patient should be withdrawn from the study treatment if, in the opinion of the investigator, it is medically necessary, or if it is the wish of the patient's primary caregiver(s). During the informed consent process, the investigator will clarify that it is essential for the patient's safety to be willing to comply with the study protocol requirements, including study safety and immunogenicity assessments following a potential withdrawal of study treatment.

When a patient is withdrawn from study treatment, the date and time of the last SOBI003 infusion and the date and reason for treatment withdrawal should be clearly described in the relevant sections of the case report form (CRF). If a patient is removed from treatment because of an AE, the reason for treatment withdrawal should always be stated as 'AE' irrespective of whether this was the investigator's or the patient's primary caregiver(s) decision.

After treatment withdrawal, efficacy, safety, immunogenicity and PK assessments should be completed as soon as possible and repeated 30 to 40 days after the last SOBI003 administration, as specified for "Early Termination" in the Schedule of Events (Table 2).

When possible, study assessments (excluding SOBI003 infusion) of Weeks 38, 52, 78 and 104 should continue in accordance with the Schedule of Events (Table 2) in order to collect continuous immunogenicity, safety and efficacy data for study patients following withdrawn treatment. Additional safety assessments will be performed at the discretion of the investigator, as warranted by the AE(s) leading to treatment withdrawal.

A patient that is withdrawn from study treatment due to an AE, should be followed up until the AE(s) leading to treatment withdrawal are either resolved or have stabilized even after the patient's participation in the study is over. Each clinically significant abnormal laboratory value or other clinically meaningful abnormality should be followed until the abnormality resolves or until a decision is made that it is not likely to resolve. Should the 30 to 40-day post last infusion be ADA-positive, then the ADA titer will be determined and ADA samplings will continue at approximately monthly basis until the ADAs have disappeared or titers have stabilized at a lower level. Every time an ADA sample is taken, a corresponding PK assessment is done.

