**Table 2 Schedule of events – Overview Enrolment to End of Study**

Week	Enrolment and treatment period (Week 25 to 104)					ET a
	25	38	52	78	104/ END	
Informed consent	X					
Eligibility criteria	X					
Concomitant therapy	X					X
Physical examination b	X					X
Neurological examination			X		X	X
Height & head circumference			X		X	X
Weight c	X					X
Vital signs d	X					X
12-lead ECG			X		X	X
Antihistamine e	X					
SOBI003 administration f	X					
Adverse events	X					X
Anesthesia/sedation g for:						
CSF sampling (PK, ADA, HS)			X		X	
CSF sampling (future research) h			X		X	
MRI (brain, liver, spleen)			X		X	
Blood sampling for:						
Safety laboratory		X	X	X	X	X
Immunogenicity		X	X	X	X	X
HS		X	X	X	X	X
PK		X	X	X	X	X
Future research h			X		X	
Urine collection for:						
Safety laboratory (Dipstick)		X	X	X	X	X
HS		X	X	X	X	X
Actigraphy (sleep pattern) i			X		X	
BSID-III/KABC-II (neurocognition, language, motor function) j			X		X	X
Parent/caregiver questionnaires:						
VABS-II			X		X	X
CSHQ i			X		X	
PedsQL, incl. Family Impact Module			X		X	X

a In case of Early Termination (ET) of SOBI003 administrations, the assessments should be completed as soon as possible after decision of treatment withdrawal.

b General appearance and skin at the infusion site are examined prior to start of each infusion and within 1 hour of completion of each infusion. On Weeks 52 and 104, as well as at Early Termination, a complete physical

examination (general appearance, skin (including potential reactions around the infusion site), eyes, ears, nose, neck, lymph nodes, throat, heart, lungs, abdomen, musculoskeletal system and extremities) is conducted.

c During the treatment period, body weight is assessed at approximately 4-week intervals to determine the actual SOBI003 dose to be administered. Weight is therefore obtained prior to preparation of the SOBI003 infusions solution at Enrolment (Week 25) and every 4th week during the study. The weight is obtained either the day prior to the infusion or the day of infusion.

d Vital signs includes blood pressure, heart rate, body temperature, respiratory rate and oxygen saturation measured by pulse oximetry. At each infusion, assessments are done pre-infusion, mid-infusion and within 1 hour after end of infusion. If dose is adjusted, vital signs are measured according to 7.5.5.4.

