#### 7.5.1.8 Early withdrawal from treatment/study

If the patient is withdrawn from study treatment, the patient should be examined as soon as possible after making the withdrawal decision. AEs and use of concomitant medications are captured. Blood is collected for safety laboratory, HS, immunogenicity and PK assessments. Urine is collected for safety laboratory and HS assessments.

Vital signs are assessed, and a neurological and a physical examination are performed. An ECG is conducted, and height, weight and head circumference are obtained.

The VABS-II is assessed by parent/caregiver (refer to Section 7.5.3.2). The parent/caregiver completes the PedsQL questionnaire.

Based on the patient's developmental age, as determined by the VABS-II score, the BSID-III and/or KABC-II tests are conducted for assessment of neurocognition, language and motor function (see Sections 7.5.3.1, 7.5.3.2, and 7.5.3.6, respectively). If *both* BSID-III and KABC-II should be assessed, then the BSID-III should be administered 2 days prior to the completion of KABC-II.

When possible, study assessments (excluding SOBI003 infusion) of Weeks 38, 52, 78 and 104 should continue in accordance with the Schedule of Events. At minimum, the Early

Termination assessments should be repeated 30 to 40 days after the last SOBI003 administration. Patients with ADA-positive samples should continue to be followed in accordance with Sections 7.5.4.3 and 7.5.5.1.

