## **7.5.3 Efficacy assessments**

### **7.5.3.1 Neurocognition**

Neurocognition is assessed at Weeks 52 and 104, and during Early Termination, by use of the neurocognition domain of the BSID-III and/or the KABC-II Nonverbal Index (NVI).

The selection of neurocognitive assessment method is done at the baseline assessment of the FIH study ([SOBI003-001](#)) based on the algorithm presented in Table 11. The neurocognitive test(s) applied in the FIH study should also be used in the extension study.

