treatment interaction as fixed factors, baseline age as covariate and an unstructured covariance matrix will be used to estimate the covariance pattern. The primary efficacy analysis set will thus consist of all patients included in this extension study (patients treated with SOBI003) and 14 patients from the NH study (untreated patients). The null hypothesis of no treatment effect will be tested with a significance test for the treatment\*time-effect, in the second step of the multiple testing procedure (see Section 9.4.5) The difference between 104 weeks and baseline will be used as the contrast of interest for the test.

All missing DQ values will be imputed. For a patient who stops treatment, let  $tp$  denote the turning point, i.e. the time point when the patient stops treatment. The patient's assessments as well as the time points for prediction are classified as being on either side of the turning point or at the turning point: prior to  $tp$ , at  $tp$ , or after  $tp$ . For patients who does not stop treatment, let  $tp = \infty$ , i.e. every time point is considered as prior to the  $tp$ . Let  $v$  denote a missing value to be imputed for a patient. The imputations will be based on two categories of predictions.

1) If the patient has two or more observations on the same side of  $tp$  as  $v$  (including a possible observation at  $tp$ ), then  $v$  is considered as *exclusively patient-predictable* ( $p_1$ ), i.e. it can be predicted by simple linear regression based only on the patient's data (intra -or extra-polation). On the other hand, if only one or zero observations exists on the same side of  $tp$  (from the particular patient) as  $v$  (including a possible observation at  $tp$ ), then it is considered as *non-predictable exclusively* from the patient's data.

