All missing values will be imputed. For a patients who stops treatment, let tp denote the turning point, i.e., the time point when the patient stops treatment. The patient's assessments as well as the time points for prediction are classified as being on either side of the turning point or at the turning point: prior to tp , at tp , or after tp . For patients who does not stop treatment, let $tp = \infty$, i.e., every time point is considered as prior to the tp . Let v denote a missing value to be imputed for a patient. The imputations will be based on two categories of predictions.

1). If the patient has two or more observations on the same side of tp as v (including a possible observation at tp), then v is considered as *exclusively patient-predictable* (p_1), i.e., it can be predicted by simple linear regression based only on the patient's data (intra-or extrapolation). On the other hand, if only one or zero observations exists on the same side of tp (from the particular patient) as v (including a possible observation at tp), then it is considered as *non-predictable exclusively* from the patient's data.

2) The other type of prediction (p_2), will be calculated by the use of a population derived slope, estimated based on the repeated measures model in Section 14.1 (without imputations), and a patient observation. There will be two cases: If the patient has one or more observations on the same side of tp as v (including a possible observation at tp), then the nearest observation will be used together with a slope, which is based on the population (treated or untreated) of the same

status as the side of tp where the prediction time point is situated, as well as the interval relative the visits which contain the prediction time point. The other case is when there is no observation on the same side of tp as v (and no observation at tp). In this case, a prediction at tp will first be calculated, based on the same method as described above (under 2) but on the other side of tp , i.e., the nearest observation relative tp on the other side of tp will be used together with a slope based on the population (treated or untreated) of the same status as the side of tp where this nearest observation time point is situated, as well as the interval relative the visits which contain the tp . This prediction at the tp is in then used to predict v as described under the first case (under 2).

For each missing value v , the following algorithm is used to impute v by i .

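### Two Early Termination cognitive tests about a month apart can set the slope used to impute a missing Week 104 DQ, because the rule has no minimum time span

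*SAP*

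**What the plan says.** **Testing after a stop.** Table 2 of the protocol marks BSID-III/KABC-II in the ET column, and section 7.5.3.1 agrees: "Neurocognition is assessed at Weeks 52 and 104, and during Early Termination". A footnote to Table 2 sets the timing of the first ET visit: "the assessments should be completed as soon as possible after decision of treatment withdrawal". Section 7.3.3.1 then asks for a second round: "efficacy, safety, immunogenicity and PK assessments should be completed as soon as possible and repeated 30 to 40 days after the last SOBI003 administration". Section 7.3.3.2 says the same for withdrawal from the study, and section 7.5.1.8 makes the repeat the minimum: "Termination assessments should be repeated 30 to 40 days after the last SOBI003 administration". Scheduled assessments, including Weeks 52 and 104, are to continue after a stop where possible.

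**Imputation.** SAP 14.1 and protocol 9.4.4.1 give the same rule. A missing value v falls before or after the turning point tp, the time treatment stopped. The condition for using the child's own line is "If the patient has two or more observations on the same side of tp as v". The value is then treated as one for which "it can be predicted by simple linear regression based only on the patient's data", and extrapolation is allowed. Call this p1. The alternative, p2, starts from one score: "then the nearest observation will be used together with a slope". After tp that slope comes from the untreated population. When p1 exists, the imputed value is a weighted average of p1 and p2. The weight on p1 falls with lambda, the months from the missing visit to the nearest observed score.

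**The concern.** The two ET scores both lie at or after tp and at most about 40 days apart. Two points satisfy the condition for p1 and leave no residual degrees of freedom. The weight on p1 takes account of how far ahead the prediction reaches, but not of how short an interval the slope was measured over. A difference between two tests a month apart, whether test noise or familiarity with the test, is therefore extrapolated over several months.

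The value affected is the Week 104 DQ of a child who stopped treatment, which is the case the turning-point rule was written for. With 9 to 12 treated children, each imputed value carries weight in the main DQ analysis.

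**Working it through.** **Inputs from the documents**
- Timing of the two ET tests: protocol 7.3.3.1, 7.5.1.8 and Table 2.
- Imputed value i = w1·p1 + (1 − w1)·p2, with w1 = exp(−lambda·ln2/3) = 2^(−lambda/3): SAP 14.1.
- Untreated decline of 30.4 DQ points in 24 months, so 15.2 per year or 1.267 per month: protocol 9.1. A straight line stands in here for the model's slope.
- Nine treated children and a planned difference of 30.4 − 9.8 = 20.6 points: SAP 7.1.

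**Assumptions.** For the table: ET tests on days 7 and 35 after the last dose (28-day gap) and a missing Week 104 test due on Day 7 of that week. For the example: a 3-point retest gain, tests one month apart and lambda 6 months. None of these figures is in the documents.

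**The SAP's own weights.** 2^(−3/3) = 0.50 at 3 months and 2^(−12/3) = 0.0625 at 12 months. Both stated figures (equal weight at three months, nearly 6% at about one year) reproduce.

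**Formula.** Let y1 and y2 be the two ET scores, D months apart, with Week 104 lambda months after y2.
- p1 = y2 + (lambda/D)(y2 − y1)
- p2 = y2 + slope × lambda
- i = y2 + k(y2 − y1) + (1 − w1) × slope × lambda, where k = (lambda/D)·2^(−lambda/3)

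A shift in y2 enters multiplied by 1 + k. Independent noise of equal SD in the two tests enters multiplied by √((1 + k)² + k²). Under p2 alone both factors are 1.

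**By week of last dose (28-day gap)**

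| Last dose | Shift × | Noise × |
|---|---|---|
| Week 25 | 1.35 | 1.40 |
| Week 40 | 1.62 | 1.74 |
| Week 53 | 1.97 | 2.20 |
| Week 60 | 2.20 | 2.50 |
| Week 70 | 2.53 | 2.95 |
| Week 78 | 2.71 | 3.21 |
| Week 85 | 2.69 | 3.17 |
| Week 93 | 2.19 | 2.49 |
| Week 97 | 1.61 | 1.73 |

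For Week 78: lambda = 5.03, D = 0.92, w1 = 0.313, so k = (5.03/0.92) × 0.313 = 1.71.

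**By gap between tests.** k is largest at lambda = 3/ln2 = 4.33 months, where k = 1.59/D. The peak factors (shift/noise) are 2.2/2.5 for 40 days, 2.6/3.1 for 30 days, 3.1/3.8 for 23 days and 4.0/5.0 for 16 days.

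**With a post-stop Week 52 score.** The line then has three points, and the noise factor falls to about 1.1 to 1.6.

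**Example**
- First ET score 50. Expected one month later off treatment: 50 − 1.267 = 48.73. With the 3-point gain: 51.73.
- p1 = 51.73 + 6 × 1.73 = 62.1
- p2 = 51.73 − 6 × 1.267 = 44.1
- w1 = 0.25, so i = 0.25 × 62.1 + 0.75 × 44.1 = 48.6
- Expected without the gain: 50 − 7 × 1.267 = 41.1
- Excess: 48.6 − 41.1 = 7.5 points, or 7.5/9 = 0.8 on a nine-patient mean

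Of the 7.5 points, 3.0 would remain under p2 from the repeat score. The two-point line adds the other 4.5 (4.5/9 = 0.5 on the mean).

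**The case against.** **The scenario is narrow.** A child must stop, complete both ET cognitive tests and then lack Week 104, although the protocol asks for that visit after a stop where possible. This stands; the documents give no expected number of such children.

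**ET scores may not count.** The SAP never says that off-schedule scores are observations, and it sets assessments more than two weeks early or late to missing. The ambiguity is real. Counting them is still the natural reading. Cognition is scheduled only at Weeks 52 and 104 in the extension, so for a missing Week 104 after a stop, at most one scheduled score can lie after tp. The two-observation condition could then never be met without ET scores. ET visits also have no target week against which to be early or late.

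**Sensitivity analyses bypass the rule.** The no-imputation, DQ = 0 and tipping-point analyses in SAP 14.1.1 do not use p1, so a result driven by this rule could be exposed. That limits the damage, but the main analysis still uses the rule.

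**Stronger readings that the documents do not support**
- *The rule biases the comparison towards SOBI003.* Noise acts in either direction. Only a retest gain would favour SOBI003, and no such gain, or its size, appears in the documents.
- *Every child who stops is affected two- to threefold.* The factor depends on when the child stops, on the gap between tests and on whether Week 52 was attended.
- *A rise from 50 to 53 is a 3-point gain, with an excess of 10.7 points.* The comparison course falls 1.27 points in that month, so such a rise implies a retest effect of 4.27 points (2.5 × 4.27 = 10.7).
- *The repeat contaminates scheduled scores for any stop near Week 52 or 104.* For stops at Weeks 49–50 or 101–102, the repeat falls after the scheduled Day 7 test.

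**Conclusion.** The gap is real and follows from the documents: p1 has no minimum time span, and its weight ignores how short the slope's baseline is. The range of about 2 to 2.7 for a shift and 2.2 to 3.2 for noise holds when Week 104 is missing, ET scores count, the last dose falls at about Weeks 53 to 93 and the tests are about four weeks apart. The shift factor is about 1.3 to 1.9 for earlier or very late stops, and both factors rise as the gap shortens.

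For one child the error can be large enough to replace an expected decline with near stability. In the example, 48.6 is imputed from a first ET score of 50. On the arm mean, one such child matters little against the planned 20.6 points. The point warrants a correction before database lock and does not by itself undermine the study. CSF HS shares the imputation method but is not exposed to this problem, because Table 2 has no CSF sampling at ET.

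**What to change.** In SAP 14.1 and protocol 9.4.4.1:

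1. State that ET scores count as observations.
2. Allow p1 only when the observations on that side of tp span a pre-specified minimum, for example 6 months. The threshold is a judgement, to be set before database lock.
3. Otherwise use p2 from the nearest observation, leaving out the 30 to 40 day repeat cognitive score. A post-stop Week 52 score is then still used where it is nearest. In the example the imputed value becomes 50 − 7 × 1.267 = 41.1.

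Leave the ET testing schedule as it is. Dropping or waiving those tests would give up off-treatment data and could leave a child with no score after the stop.

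The cost is a sentence or two in each document. At most one closely spaced score per withdrawn child goes unused in the imputation.

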### 5.1.3 SOBI003 nonclinical development

In a MPS IIIA mouse model with a spontaneous missense mutation of the *SGSH* gene, disease manifestations similar to the human conditions are obtained, including lysosomal storage of HS and neurological pathology. In these mice, repeated i.v. administration of SOBI003 resulted in a dose and time dependent clearance of HS in brain. The reduction in HS translated into improvements in terms of lysosomal size and neuroinflammation as well as beneficial effects on behavioral impairments.

HS reduction in cerebrospinal fluid (CSF) correlated with reduction of HS in whole brain of MPS IIIA mice following repeated i.v. administration of SOBI003, thus supporting the use of HS reduction in CSF as a biomarker of disease modification.

In MPS IIIA mice, a relationship between treatment effect and SOBI003 dose level and treatment duration was observed. The reduction of HS in brain was related to the accumulated active SOBI003 dose. The return to baseline HS biomarker levels after discontinuation of treatment was also a gradual process in this mouse model. To quantify and understand the dose, time, concentration and effect relationship in MPS IIIA mice, a semi-mechanistic in silico model was developed based on mouse PK, distribution of SOBI003 to the brain, SOBI003 entering target cells, the intracellular retention of SOBI003 and an intracellular SOBI003 concentration-effect relationship on HS reduction. Human fibroblasts of an MPS IIIA patient (27) were used for in vitro determination of SOBI003 cell entry rate, cell retention, and intracellular concentration-effect relationship. Allometric scaling from rat and cynomolgus monkey to human was applied to predict clearance and volume of distribution in patients (body weight 20 kg). Translating the mouse in silico model to human repeated weekly administration of 3 mg/kg, SOBI003 is predicted to gradually achieve a brain HS reduction of ~ 35 % after 3 months and ~ 45 % after 6 months treatment. Thus, according to model-based simulations using the in silico model, the 3 mg/kg dose level is expected to gradually elicit a pharmacological effect in CNS in humans. Repeated weekly administration of 10 and 20 mg/kg SOBI003 is predicted to achieve a brain HS reduction of ~ 75 % and ~ 80 % after 3 months and ~ 80 % and ~ 85 % respectively after 6 months treatment relative to baseline.

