### **9.4.4 Analysis related to secondary objectives**

#### **9.4.4.1 Key secondary endpoints at Week 104**

The first key efficacy endpoint related to the first key secondary objective is the change from baseline in Development Quotient (DQ) of neurocognitive development at Week 104 after start of SOBI003 treatment in the FIH study (SOBI003-001). Since this is a single-arm study without an internal control group, efficacy relating to neurocognition will be evaluated through a comparison to an external historical control group consisting of the available natural history data within the target study population, i.e. 14 patients with a rapid progressive disease and a baseline age of 12 to 72 months followed for 24 months (22).

The Bayley Scales of Infant and Toddler Development, Third Edition (BSID-III) or the Kaufman Assessment Battery for Children, Second Edition (KABC-II) will be used to assess neurodevelopment using the same approach as in the NH study (22). For each patient, an age-equivalent score (AEq) is determined using published normative data for the US population. An AEq score is the average score for a particular age. The Development Quotient is calculated as the AEq divided by the chronological age of the child multiplied with 100, i.e.  $DQ = 100 * AEq / Age$ .

For patients completing an assessment of both BSID-III and KABC-II, the BSID-III score will be used as a basis for calculating the DQ of neurocognitive development at baseline. A calibration of overlapping AEq scores between BSID-III and KABC-II will be done to assess if a patient outgrows the BSID-III test during the duration of the study. If confirmed, assessments of KABC-II will form the basis for calculating DQ of neurocognitive development for remaining study assessments.

DQ of neurocognitive development will be evaluated using a repeated measures analysis with the DQ measurements at baseline, Week 52, and Week 104 as response, and visit and visit-

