The second key efficacy endpoint related to the second key secondary objective is the change from baseline in HS levels in CSF at Week 104 after start of SOBI003 treatment in the FIH study (SOBI003-001).

For the purpose of the multiple testing procedure (see Section 14.3), the linear repeated measures analysis with untransformed HS levels in CSF will be used, identical to the DQ analysis with the exception of the treatment factors.

The time effect is used to judge the HS level change in CSF. The null hypothesis of no change will be tested with a significance test for the time-effect in the first step of the multiple testing procedure (see Section 9.4.5). The difference between 104 weeks and baseline will be used as the contrast of interest for the test. Missing HS values will be imputed according to the same methodology as for the missing DQ values.

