14.1 The DQ endpoint

One of the key secondary objectives is to assess the effect of SOBI003 on neurocognition, as compared to untreated MPS IIIA patients from a NH control. The key endpoint related to this

objective is the change from baseline in DQ of neurocognitive development at 104 weeks of treatment, and will be estimated by a model based contrast.

To address the efficacy objective, a repeated measure analysis will be utilized where DQ is the response variable and time, baseline age, time*baseline age and treatment*time are fixed effects and the dependency between observations within the same patient is represented by an unstructured variance-covariance matrix.

The time window is two weeks, i.e., if the assessment is more than two weeks too early or more than two weeks too late, then the DQ is set to missing for that assessment.

In the NH study, a simple linear regression model was used, i.e. with DQ as the response variable and the age of the child as dependent variable (Shapiro et al 2016). As the aim in this clinical development program is to demonstrate that treatment with SOBI003 is efficacious and the effect of treatment is dependent on the time the patient has been treated, this model needs to be adopted so that time and baseline age are factors rather than the actual age of the child (which is the sum of the baseline age and the time in study). The results from the NH study suggest that the decline in DQ is not linear across all ages, and an interaction term time*baseline age is planned to be included in the model to allow for such a non-linearity. Also an unstructured variance-covariance matrix is planned to be used to account for the dependency between observations within the same patient. As a further justification for the model, it should be noted that time, baseline age and time*baseline age are all significant factors in the NH study.

To represent the treatment effect without constraint to a specific relation across visits, a term treatment*time is planned to be included in the model. This effect is used to judge the treatment effect. The null hypothesis of no treatment effect will be tested with a significance test for the treatment*time-effect in the second step of the multiple testing procedure (see Section 14.3). The difference between 104 weeks and baseline will be used as the contrast of interest for the test.

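### The population-slope imputation applies one interval's slope to a gap that crosses Week 52, so an imputed Week 104 DQ or CSF HS value is wrong whenever the two interval slopes differ

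*SAP*

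**What the plan says.** Missing DQ values are imputed from two predictions. p1 is a regression on the child's own scores and needs at least two scores on the same side of tp as the missing value. p2 starts from the child's closest available score and adds a single population slope. That slope is the treated or the untreated one, depending on whether the missing value falls before or after tp, and it is further selected by visit interval: "as well as the interval relative the visits which contain the prediction time point". If there is no score on that side of tp, a value at tp is predicted first by the same method, with the slope of the interval containing tp. "This prediction at the tp is in then used to predict v as described under the first case". Without p1, p2 is used alone. Otherwise p1 has weight exp(-λ ln2/3), where λ is the months to the nearest score.

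Protocol 9.4.4.1 has the same rule, names the model's visits ("DQ measurements at baseline, Week 52, and Week 104 as response") and extends the method to the other confirmatory endpoint: "Missing HS values will be imputed according to the same methodology as for the missing DQ values". SAP 9.1 also imputes both DQ and CSF HS.

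The model leaves the visit means free. SAP 14.1 includes treatment*time "To represent the treatment effect without constraint to a specific relation across visits", together with time and time*baseline age.

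**The concern.** The model visits define two intervals, baseline to Week 52 and Week 52 to Week 104. A missing Week 104 value lies in the second, so p2 uses the second interval's slope from wherever the nearest score happens to be. Nothing in either document adds the first interval's slope for the months before Week 52. The only chaining is at tp, and each leg there again uses one slope. The starting point must be an observation or the prediction at tp, so an imputed Week 52 value does not serve as a bridge.

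This amounts to assuming a straight line over two years, while the analysis model deliberately avoids that assumption. The imputed values enter both confirmatory tests, whose contrast is Week 104 against baseline. The children affected are mainly early stoppers with no Week 52 score, whom the imputation is meant to handle.

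**Working it through.** **Plan's own figures.** Weight on the child's own data, exp(-λ ln2/3): 50% at 3 months and 6.25% at 12 months, as SAP 14.1 states (nearly 6% at a year). At 16 months it is 2.5%. So p2 carries about 94% or more of any imputation from a year away, and all of it when p1 does not exist. HS power (paired t, n = 9, fall 0.8 × 5.2 = 4.16, SD of change 1.8 × √(2 × 0.9) = 2.41) is 99.4%, against the stated 99%.

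**Error formula.** Let m be the month of the last score (or tp) and let s1 and s2 be the monthly changes in the two intervals.
- Rule as written: (24 − m) × s2.
- Following the fitted profile: (12 − m) × s1 + 12 × s2.
- Error: (12 − m) × (s2 − s1). It is zero if s1 = s2 or if a Week 52 score is available as the starting point.

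**DQ.** SAP 7.1 gives two-year declines of 30.4 (untreated) and 9.8 (assumed, treated). The split between years is not given. I assume that 35-65% falls in year 1, so the slopes differ by at most 0.30 × decline / 12:
- untreated: 0.30 × 30.4 / 12 = 0.76 points per month;
- treated: 0.30 × 9.8 / 12 = 0.245 points per month.

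| Case, Week 104 missing | Months to Week 52 | Largest error, either sign |
|---|---|---|
| Stops at Week 24, no later score (untreated slope from tp) | 28/52 × 12 = 6.46 | 6.46 × 0.76 = 4.9 |
| Single post-stop test at month 7 (untreated slope) | 5 | 5 × 0.76 = 3.8 |
| Still treated, baseline score only (treated slope) | 12 | 12 × 0.245 = 2.9 |

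One child in nine with an error of 4.9 moves the treated mean by 4.9 / 9 = 0.5 points, against an assumed difference of 30.4 − 9.8 = 20.6.

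**CSF HS.** Baseline is 5.2 and the Week 104 target is 1.04. Protocol 5.1.3 expects most of the fall early: brain HS at the two higher doses is "predicted to achieve a brain HS reduction of ~ 75 % and ~ 80 % after 3 months", and Protocol 7.5.6.3 expects CSF to mirror brain. Let g be the assumed share of the fall reached by Week 52. From baseline only, the rule gives 5.2 − 24 × (1 − g) × 4.16 / 12:
- g = 0.8: 3.54;
- g = 0.9: 4.37;
- g = 1: 5.20, i.e. no reduction.

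If k of 9 children were imputed at their baseline value, the mean change would go from −4.16 to −3.70 (k = 1), −3.24 (k = 2) or −2.77 (k = 3). Simulated step 1 power goes from 99.5% to 98.5%, 95.7% and 89%. If instead a FIH value of 1.04 at Week 24 is the nearest observation and the plateau slope is 0, the rule gives 1.04, which is correct.

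**The case against.** The case against concerns mainly size, and much of it stands.

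- A reader might infer a DQ error of about 9 points (12 × 0.76 = 9.1) by running the untreated slope from baseline. The documents describe no such child. Entry requires completion of the 24-week FIH study, so a treated child's tp is at Week 24 or later, and the 14 natural history patients are described as followed for 24 months.
- A reader might infer that a treated drop-out is generally imputed with no HS reduction. That needs a child with no usable CSF value after baseline. Protocol 7.2 refers to CSF HS reductions observed in the FIH study, and SAP 5.2 pools FIH efficacy data with the extension. The plateau itself rests on a model-based prediction for brain, and doses may change during the extension.
- A reader might take "The results from the NH study suggest that the decline in DQ is not linear across all ages" as proof that the yearly mean declines differ. It concerns age, and the time*baseline age term addresses it. The argument here needs only that the model does not force the two slopes to be equal.
- A value missing exactly at Week 52 belongs to both intervals, and baseline and Week 104 may be equally near. This looks serious but does not alter the Week 104 contrast. Under the SAP model with complete data and unstructured covariance, every visit has the same regressors, so the contrast reduces to least squares at Week 104 and at baseline.
- After treatment withdrawal, Protocol 7.3.3.1 asks for early-termination testing, a repeat at 30 to 40 days and, when possible, the Week 52 and 104 assessments. A Week 52 score removes the error.
- SAP 14.1.1 and 14.2.1 plan analyses without imputation and tipping-point analyses, plus DQ = 0 for missing DQ. These show whether a conclusion depends on the imputed values. They do not correct the values used in the confirmatory tests.

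None of this changes what the rule computes when the gap crosses Week 52.

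**Conclusion.** The defect is real and moderate. Followed exactly, the rule gives a wrong Week 104 value whenever the last score or tp precedes Week 52, Week 104 is missing and the interval slopes differ.

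For DQ the error is at most about 4.9 points for a child stopping at Week 24, 3.8 for a single post-stop test at month 7, and 2.9 for a treated child with baseline only. Its direction is unknown. These figures rest on the assumed 35-65% split and would grow with a more uneven one. The error is nil when Week 52 is observed and treatment continues.

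For CSF HS the error is large, up to 5.2 against 1.04, only if baseline is the sole usable CSF value, and it then works against the drug. It is small if a FIH value already on the plateau counts as an observation. The documents do not say which FIH visits count for this purpose.

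**What to change.** Define p2 as the nearest own observation plus the population change over every interval crossed:

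p2 = y(t_obs) + M(t_v) − M(t_obs),

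where M is the model-estimated mean profile, joined between visits and evaluated at the child's baseline age, since the SAP model contains time*baseline age.

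- **DQ:** switch from the treated to the untreated profile at tp.
- **CSF HS, visit grid:** make the FIH CSF visits interval boundaries and state that their values count as observations. A straight baseline-to-Week 52 line would take a Week 24 value of 1.04 to 1.04 − 4.16 × 28/52 = −1.2, which is impossible.
- **CSF HS, after stopping:** state which HS profile applies after tp. It cannot be an untreated one. The HS model has no treatment factor, and SAP 8.2 brings natural history patients into the FAS only for the DQ analyses.
- **Minor:** state which interval a value exactly at Week 52 belongs to, and average the predictions from equally near observations.

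The cost is a few lines in SAP 14.1 and Protocol 9.4.4.1 and a small change to the imputation program before database lock. No new data are needed.
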